2.4.6 Analyses of pharmacokinetic and pharmacodynamic variables

2.4.6.1 *Analyses of pharmacokinetic variables*

Descriptive statistics and listings

All summaries/plots of PK parameters will be based on the PKPD efficacy population.

Separate summaries based on the PK population may be provided if considered useful (if PK and PKPD efficacy populations are different).

Pharmacokinetic parameters of ferroquine, its metabolite SSR97213 and OZ439 compounds will be summarized by descriptive statistics (such as arithmetic mean, geometric mean, median, SD, SEM, CV, minimum, and maximum) for each group (FQ alone, FQ/OZ439).

Box-and-whisker plots will be provided for each treatment group and compound (FQ, SSR97213 and OZ439), representing mean, median, quartiles and outlying observations.

Individual metabolic ratios (FQ/SSR97193 considering molecular weight of each moiety) will be computed for C_{max} , $AUC_{0\text{-Day}28}$ and AUC listed and summarized for each treatment group.

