AEs	←====	=====	-==	====	====		====		====	====		====	====	=====			=====	=====	=====	====	\Rightarrow	
Laboratory testing																						
Clinical laboratory safety ^h	Х											Х	(X)	(X)			Х		Х	Х	Х	72 and 96 h post-dose if participant still hospitalized

		Т	rea	tme	ent	Pe	rio	d a	nd p	ost-t	reatn	nent s	surve	illand	e (D	ays)		F	ollow	-up (Days)		
Procedure	Screening (up to 1					06	9					1		2	3	4	5	6	7	10	14	21	28 ±2	
Procedure	day before Day 0)										Ног	ırs po	st-dos	е					11	1	±1	± 2	±2	Notes
	,	0	1	2	4	6	8	3	12	18	24	30	36	48	72	96	120	144	168					
Visit	1 ^b					2						3		4	5	6	7	8	9	10	11	12	13 ^C	
Viral hepatitis serology	Х		1					-																rapid spot test (HAV IgM, HBsAg, HCV Ab), and/or HCV RNA (if known)
Pregnancy test	Х																						Х	Urine beta-HCG is the minimum acceptable test. Result must be confirmed negative prior to dosing.
PK OZ439 ^j		Х	Х	Χ	Х	Х			Х		Х			Х	Х		Х		Х		Х			Not measured in Arm A; Plasma samples
PK FQ (+metabolite) ^j		Х	Χ		Х	Х	()	X	Χ		Х				Х				Х		Х		Х	

- a Day 0 is defined as the day of single dose treatment to comply with WHO guidelines (2).
- b Visit 1 may occur on the same day as Visit 2 provided that all baseline assessments and biology results (including parasitemia and laboratory safety) are obtained before patient randomization.
- c In case of study discontinuation, all assessments planned on Day 28, including rescue therapy administration, should be performed as far as possible.
- d Administered at Day 28 for participants who reach Day 28 without having received a rescue medication. At each contact post-dosing, conditions for treatment failure will be assessed and rescue therapy will be given accordingly. See details in Section 7.7.1.

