10.2 POPULATIONS FOR ANALYSES

For purposes of analysis, the following populations are defined (Table 7):

Table 7 - Populations for analyses

Population	Description	
Screened participants	All participants who sign the ICF and met the inclusion criteria	
Randomized participants (intent to treat [ITT])	All participants with a treatment kit number allocated and recorded in IRT database at Visit 2 (Day 0), and regardless of whether the treatment kit was used or not	
Evaluable (modified ITT [mITT])	All randomized participants with parasitologically confirmed malaria at baseline, who received at least the single administration of OZ439/FQ 400 mg and who have parasitemia data post-randomization. Participants will be analyzed according to the treatment arm allocated by randomization	
Safety	All randomized participants who take at least 1 dose or part of a dose of the single administration OZ439 & FQ 400 mg. Participants will be analyzed according to the treatment they actually received	
PK	All participants included in the Safety population with at least one evaluable blood sample for PK post IMP administration and with adequate documentation of date of dosing and date of sampling	
PK/PD	All participants included in both the mITT population and the PK population	

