10.3.3 PK analyses

All PK analyses will be performed on the PK Population (see Table 7). The PK analyses are summarized in Table 10.

Table 10 - PK analyses

Endpoint	Statistical Analysis Methods	
For secondary objectives		
 Concentrations 	Descriptive statistics by treatment arm and by time point	
 PK parameters 	 Descriptive statistics (such as arithmetic mean, geometric mean, median, SD, SEM, coefficient of variation, minimum, and maximum) for each treatment arm 	

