2.3.4 Pharmacokinetics population

The PK population includes all patients in the safety population with at least one evaluable blood sample for PK of either OZ439 or FQ post IMP administration and with adequate documentation of date of dosing and date of sampling.

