2.3.5.1 PK/PD efficacy population

The PK/PD efficacy population will be the primary efficacy population.

Pharmacokinetic/pharmacodynamics (PK/PD efficacy) population will include those patients in both the PK and mITT populations with additional criteria specified below,..

Patients need at least one evaluable blood sample for PK of both OZ439 and FQ.

Parasitemia data for patients with rescue treatment started before the considered time point will be excluded from this time point until Day 28.

In case of vomiting or other reasons interrupting the administration of the complete dose, and if valid parasitemia data post-randomization available, then patients will be included in the PK/PD efficacy population.

As defined in [Section 2.1.4.1](#), there are certain criteria that would exclude patients from having an evaluable PCR-corrected ACPR at Day 28::

- Other species infection without *P. falciparum* reemergence
- Lost to follow-up,
- Withdrawal,
- Protocol violation.

Protocol violations considered above are those potentially impacting efficacy assessments at Day 28:

- Patients who needed rescue treatment because they did not take IMP or due to vomiting during IMP administration.
- Patient presenting severe malaria or receiving a rescue treatment due to severe malaria during the first 24 hours following IMP start (i.e. wrong inclusion).
- Start of rescue therapy before Day 28 assessment not due to: vomiting during IMP administration, wrong inclusion, treatment failure (per investigator or per WHO criteria), or other species infections.
- Missing baseline parasitemia, and positive parasitemia at 48 or 72 hours.
- Intermittent missing or out of window post-baseline parasitemia preventing to evaluate ACPR Day 28.
- Missing post-baseline body temperature preventing to evaluate ACPR Day 28.
- Out of Day 28 time window parasitemia preventing to evaluate ACPR Day 28.
- Patients with at least one enrolment violation among the following:
 - Patients who meet exclusion criteria E 01 which is: “Presence of severe malaria (according to WHO definition)”.
 - Patients violator for inclusion criteria I02 which is: “Presence of *P. falciparum* malaria, with a fever as defined with axillary temperature ≥ 37.5 degree Celsius ($^{\circ}\text{C}$) or oral/

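### SAP 2.4.6.1 puts the PK-parameter summaries on a population whose two-drug sample rule, read literally, leaves out the FQ-alone arm that the same section promises to summarise

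*SAP*

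**What the plan says.** On the population for PK parameters, SAP 2.4.6.1 says: "All summaries/plots of PK parameters will be based on the PKPD efficacy population". It then plans descriptive statistics "for each group (FQ alone, FQ/OZ439"), with box plots and metabolic ratios by treatment group. The PK population appears only as an option: "Separate summaries based on the PK population may be provided if considered useful (if PK and PKPD efficacy populations are different").

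On who belongs to the PK/PD efficacy population, SAP 2.3.5.1 takes patients who are in both the PK and mITT populations and adds: "Patients need at least one evaluable blood sample for PK of both OZ439 and FQ". It goes on to list loss to follow-up, withdrawal, infection with another species and a set of protocol violations as reasons why Day 28 PCR-corrected ACPR cannot be evaluated.

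On OZ439 sampling, the note in the Protocol schedule of activities (section 2) reads "Not measured in Arm A; Plasma samples". The flow chart in SAP Appendix A carries the same note.

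The SAP's PK population (2.3.4) needs only "at least one evaluable blood sample for PK of either OZ439 or FQ post IMP administration". The protocol has no two-drug rule. Its PK/PD population (10.2, Table 7) is "All participants included in both the mITT population and the PK population", and for PK it says "All PK analyses will be performed on the PK Population (see Table 7").

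**The concern.** Characterising the PK of FQ and its metabolite SSR97213 is a secondary objective, and both are sampled in every arm. If the summary population needs an OZ439 sample, the arm with no scheduled OZ439 samples drops out and the promised FQ-alone column is empty. Arm A is also the only group that shows FQ exposure without OZ439.

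Two further matters follow from the choice of population. The protocol had settled it differently and SAP 1.6 does not record the change, although 1.6 does record another PK change (terminal half-life will not be estimated). And a set built around whether ACPR can be scored may drop patients whose concentrations are perfectly usable.

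**Working it through.** The main check is logical, with simple counts.

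1. **Planned size.** Protocol 10.1 plans 30 evaluable patients per arm, allows about 15% early dropout, and enrols about 35 per arm, 140 in all. Check: 30 × 1.15 = 34.5, rounded up to 35, and 4 × 35 = 140. Dividing instead gives 30 / 0.85 = 35.3, rounded up to 36, or 144 in all. The stated figures are consistent with either to within rounding.

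2. **Applying the rule.** Membership needs an evaluable OZ439 sample and an evaluable FQ sample. Scheduled OZ439 samples number 12 per patient in Arms B to D and none in Arm A (Protocol Table 3 and schedule). Through scheduled sampling, therefore:
   - Arm A: 0 of about 35 randomized, 0 of 30 evaluable.
   - Remaining: 140 − 35 = 105 randomized, 120 − 30 = 90 evaluable.
   - Share lost: 35 / 140 = 30 / 120 = 25%.

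3. **Data affected.** Each Arm A patient has 11 scheduled FQ/SSR97213 samples (Protocol Table 3): 35 × 11 = 385. Read literally, the parameters derived from these enter no mandatory PK-parameter summary.

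4. **Applying the alternative.** The PK population in SAP 2.3.4 accepts a sample of either drug. Arm A qualifies on FQ alone and all four arms return.

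5. **Knock-on for the primary analysis.** SAP 2.3 and 2.4.4 place the primary exposure-response model on the same population. An illustrative simulation used the model in Protocol Appendix 8 and SAP 1.3: logit(p) = 3.23 + 0.12·FQ + 0.73·OZ439 − 1.27·log10(parasitemia), with log10 parasitemia normal (mean 4, SD 0.55) truncated to 3.48–5.5. It used 30 per arm, a two-sided 5% Wald test and 2,000 trials per scenario. The documents do not give the Day 7 concentration distributions. Medians were therefore calibrated to the stated ACPR rates of 72%, 81%, 91% and 97%, and the coefficients of variation (CV) and a correlation of 0.2 were **assumed**.

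| Assumed CV, FQ / OZ439 | Power, four arms | Power, Arm A dropped |
|---|---|---|
| 30% / 30% | 90.0% | 49.6% |
| 40% / 60% | 92.6% | 50.6% |
| 50% / 80% | 92.2% | 53.3% |
| 50% / 100% | 90.6% | 48.9% |

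The four-arm column agrees with the plan's figure of around 90%. Simulation standard error is √(0.9 × 0.1 / 2000) ≈ 0.7 points near 90% and √(0.5 × 0.5 / 2000) ≈ 1.1 points near 50%. Like the plan's own simulation, this uses Day 7 concentration, whereas the planned analysis uses AUC.

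**The case against.** The strongest reply is that nobody meant to leave Arm A out. SAP 2.4.6.1 names an FQ-alone group, and the team may well have meant Arm A to enter with zero OZ439 exposure. That is plausible, but neither document says so, and a zero by design is not an evaluable blood sample.

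It can also be said that the PK population is available as a fallback, that the detailed Bayesian PK analyses have a separate plan and reports (SAP 2.1.6), and that Protocol 10.3 leaves the analysis populations to the SAP. These points soften the consequence. They do not guarantee the FQ-alone summary, because the fallback is discretionary. Nor do they supply the missing entry in 1.6, which says only that populations were clarified and that the primary efficacy population changed. Describing exposure in the same set as the exposure-response model would be a defensible choice once 2.3.5.1 is reworded, provided that it is declared.

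A reader might infer more than the documents support:

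- *That no Arm A patient could ever enter.* Unscheduled samples of both drugs are requested before early rescue and on QTcF or ALT events (Protocol 7.7.1 and schedule footnotes), with no stated exemption for Arm A. A few patients might qualify that way, though they would be selected on those events.
- *That FQ exposure with and without OZ439 cannot be compared.* The samples are taken in every arm, the optional PK-population summaries would show it, and the concentration/ECG plots use a PK/PD safety population with no two-drug rule. The stated objective is to characterise PK. It does not call for that comparison.
- *That exposure is described only in patients selected on outcome.* Treatment failures stay in: SAP 2.1.4.1 scores them as failures, and 2.3.5.1 does not count rescue for treatment failure as a violation.
- *That every listed exclusion is irrelevant to PK.* Not taking the study drug, or vomiting during its administration and needing rescue, bears directly on exposure.
- *That concentration summaries are also confined to this set.* The quoted sentence covers PK parameters only. SAP 2.4.6.1 names no population for concentrations by time point.

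**Conclusion.** The contradiction stands as a matter of wording. Read literally, SAP 2.4.6.1 and 2.3.5.1 together remove about 35 of 140 randomized patients (25%) from the PK-parameter summaries, and these are the whole FQ-alone arm that 2.4.6.1 undertakes to report. The move away from the protocol's PK population is not declared in SAP 1.6. If the ACPR-evaluability criteria in 2.3.5.1 act as population exclusions, some patients in Arms B to D are lost as well, for reasons such as loss to follow-up, withdrawal or other-species infection that do not by themselves make their PK data invalid. The documents do not allow that number to be estimated.

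The weight is moderate. The summaries are secondary and descriptive, and the samples are taken whatever the SAP says. The 25% rests on a literal reading and on scheduled sampling alone.

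A reader might take the fall in power to roughly 50% as the size of this point. It is not. It concerns the primary analysis, depends on assumed concentration variability and correlation, and arises only if the rule is applied to Arm A as written. Its use here is to show that the sample rule in 2.3.5.1 needs correcting at its source.

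**What to change.** Four short edits to the SAP, with no new data and no change to sampling:

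1. In 2.4.6.1, base the PK-parameter summaries and plots on the PK population of 2.3.4, as Protocol 10.3.3 does, and name the same population for the concentration summaries. Summaries on the PK/PD efficacy population can be kept as an addition.
2. In 2.3.5.1, require an evaluable OZ439 sample only in arms randomized to OZ439, and an evaluable FQ sample in all arms.
3. State how OZ439 exposure is coded in Arm A for the exposure-response model, for example AUC = 0.
4. In 1.6, list any remaining departure from the protocol's population for PK analyses.

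Edit 1 alone would restore the PK summaries but leave the primary exposure-response population with the same literal exclusion of Arm A, so edits 2 and 3 should go with it. The cost is a few sentences, plus a matching change to the population flags in the analysis programs.

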1 OVERVIEW AND INVESTIGATIONAL PLAN

1.1 STUDY DESIGN AND RANDOMIZATION

A phase 2a, randomized, open label, parallel-group study, single-dose regimen, testing 3 dose levels of OZ439 given in combination with FQ and FQ alone in participants with uncomplicated *P. falciparum* malaria.

After a screening phase of up to 1 day before the single dose administration, patients are randomized (stratified by investigative site) via Interactive Response Technology (IRT) in a 1:1:1:1 ratio to 1 of the 4 treatment groups.

Balance across a group of blocks will be achieved by considering a Latin square design feature during the generation of the randomization schedule. This approach is being used to provide better balance of study level treatment assignments as compared to conventional random of sampling for blocks.

[figure not shown]
12 blocks size (of size 8) will be attributed to each site and will be balanced across the group block entries, as well as within each block. The full randomization list will be comprised of the records which make up twelve 8 x 8 Latin squares ($12 \times 8 \times 8 = 768$ records in total). The sequence of treatment groups within each block will be random.

Approximately 140 patients (35 patients per treatment group) will be recruited and randomized in order to have 120 evaluable patients (30 patients per treatment group) from approximately 8 to 10 sites.

Adults up to 69 years old and adolescents as of 14 years old will be included in 4 parallel arms in a 1:1:1:1 randomization ratio. Randomization will occur the day of or up to 1 day after screening procedures.

Participants will receive one of the 4 treatments: FQ 400 mg alone or combined with OZ439 300 mg, 600 mg, or 1000 mg.

The graphical presentation of the study design on the single-dose treatment is provided in Figure 1.

Note: Visits 1 & 2 can occur on the same day ; Visit 13 : assessment of primary endpoint

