AEs	<=====→																							
Laboratory testing																								
Clinical laboratory safetyh	X												X	(X)	(X)			X	X	X		72 and 96 h post-dose if participant still hospitalized		
Viral hepatitis serology	X																					rapid spot test (HAV IgM, HBsAg, HCV Ab), and/or HCV RNA (if known)		
Pregnancy test	X																				X	Urine beta-HCG is the minimum acceptable test. Result must be confirmed negative prior to dosing.		
PK OZ439i		X	X	X	X	X		X		X			X	X		X		X				Not measured in Arm A; Plasma samples		

Procedure	Screening (up to 1 day before Day 0)	Treatment Period and post-treatment surveillance (Days)												Follow-up (Days)								Notes			
		0a				1	2	3	4	5	6	7	10	14 ±1	21 ±2	28 ±2									
		Hours post-dose																							
		0	1	2	4	6	8	12	18	24	30	36	48	72	96	120	144	168							
Visit	1b	2				3			4	5	6	7	8	9	10	11	12	13c							
PK FQ (+metabolite)/		X	X		X	X	X	X		X			X			X		X		X		X			

- a Day 0 is defined as the day of single dose treatment to comply with WHO guidelines (5).
- b Visit 1 may occur on the same day as Visit 2 provided that all baseline assessments and biology results (including parasitemia and laboratory safety) are obtained before patient randomization.
- c In case of study discontinuation, all assessments planned on Day 28, including rescue therapy administration, should be performed as far as possible.
- d Administered at Day 28 for participants who reach Day 28 without having received a rescue medication. At each contact post-dosing, conditions for treatment failure will be assessed and rescue therapy will be given accordingly. See details in [Section 7.7.1](#) of protocol

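### SAP 2.4.6.1 puts the numerical PK-parameter table into two groups, which read literally pools the three OZ439 doses that Protocol Table 10 keeps apart

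*SAP*

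**What the plan says.** Protocol 10.3.3, Table 10, plans PK reporting by arm. Concentrations get "Descriptive statistics by treatment arm and by time point", and the list of statistics for PK parameters ends "coefficient of variation, minimum, and maximum) for each treatment arm".

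SAP 2.4.6.1 gives nearly the same list of statistics (arithmetic and geometric mean, median, SD, SEM, CV, minimum, maximum) but attaches it to a different grouping: "for each group (FQ alone, FQ/OZ439".

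The next sentence returns to the arms: "Box-and-whisker plots will be provided for each treatment group and compound". The metabolic ratios in that section are also summarised by treatment group.

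SAP 1.1 fixes what a treatment group is. Patients are randomised in a "1:1:1:1 ratio to 1 of the 4 treatment groups" and receive "FQ 400 mg alone or combined with OZ439 300 mg, 600 mg, or 1000 mg". For OZ439 sampling, the flow chart in SAP Appendix A notes "Not measured in Arm A; Plasma samples".

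SAP 1.6 lists the statistical changes from the protocol. One concerns PK (terminal half-life is dropped). None concerns the grouping of PK summaries.

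**The concern.** One label, FQ/OZ439, covers three arms whose OZ439 doses differ by a factor of 1000/300 = 3.3. Because OZ439 is not measured in the FQ-alone arm, a two-group table leaves OZ439 with a single column in which all three doses are mixed. For FQ and SSR97213 the table would compare FQ alone with all OZ439 arms together, and would give no figures by OZ439 dose.

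Characterising the PK of all three entities is a secondary objective. A mean and CV taken over three doses describe none of them: the mean falls between the arms, and the CV adds the planned difference in dose to the variability between patients. A programmer who follows the SAP sentence to the letter would produce this table, and nothing in SAP 1.6 would show that it departs from the protocol.

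**Working it through.** The plan states no figure to reproduce here. The check is a comparison of texts, followed by an illustration.

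**1. Grouping, place by place**

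| Place | Output | Grouping |
|---|---|---|
| Protocol Table 10 | PK-parameter statistics | treatment arm (4) |
| SAP 2.4.6.1, summary sentence | same statistics | two labels |
| SAP 2.4.6.1, box plots | mean, median, quartiles, outlying values, for each compound | treatment group (4 by SAP 1.1) |
| SAP 2.4.6.1, metabolic ratios | listing and summary | treatment group |
| SAP 2.4.6.3, ECG predictions | predicted change at Cmax | each dose |
| SAP 2.4.6.3, model averaging | effect at geometric-mean Cmax | FQ 400 mg with OZ439 1000 mg |

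Only the summary sentence uses two labels. The geometric mean, SD, SEM and CV are not among the features named for the box plots, so in SAP 2.4.6.1 the table is where a reader would look for them.

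**2. What a literal pooled column would show**

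Inputs from the documents: doses of 300, 600 and 1000 mg, and 1:1:1:1 allocation. Assumptions not in the documents: exposure proportional to dose, equal numbers analysed per arm, and the same within-arm CV, *w*, in each arm, taken as 30%, 50% or 80%.

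- Mean dose = (300 + 600 + 1000)/3 = 633.3 mg.
- Between-dose SD = √[(333.3² + 33.3² + 366.7²)/3] = 286.7 mg, so the between-dose CV is 286.7/633.3 = 0.453.
- Pooled CV = √[(1 + 0.453²)(1 + *w*²) − 1].

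| Within-arm CV | Pooled CV |
|---|---|
| 30% | 56% |
| 50% | 71% |
| 80% | 99% |

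The geometric version, with log-normal exposure, leads to the same conclusion. The geometric mean of the doses is (300 × 600 × 1000)^(1/3) = 565 mg. That is 1.88, 0.94 and 0.56 times the 300, 600 and 1000 mg doses. Dose alone adds 0.243 to the log-scale variance. With geometric CV = √[exp(ln(1 + *w*²) + 0.243) − 1], within-arm values of 30%, 50% and 80% become 62%, 77% and 105%.

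**The case against.** The strongest reply is that no pooling is meant. The bracket can be read as shorthand for the two kinds of regimen, echoing the design description of OZ439 given with FQ and FQ alone. Where this SAP wants pooling it says so: SAP 2.4.4.2.5 asks for estimates pooled across the four groups and also separately by dose group. The silence of SAP 1.6 then fits a drafting slip as well as it fits an undeclared change. This stands: intent to pool is not established. It does not make the sentence safe to program from, because the literal reading gives two columns and the protocol calls for four arms.

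A reader might infer that OZ439 exposure by dose will not be reported at all. The documents do not support that. The sentence after the bracket reads: "Box-and-whisker plots will be provided for each treatment group and compound (FQ, SSR97213 and OZ439), representing mean, median, quartiles". SAP 2.4.6.3 also needs dose-specific Cmax. In addition, SAP 2.1.6 places the detailed PK analyses in a separate plan and report, which are not available here, with a summary in the main study report.

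A reader might also infer damage to the primary analysis, since it depends on the spread of OZ439 exposure. It is not touched: SAP 2.4.4.1.1 enters the AUC values as regressors and does not use the descriptive table. Nor can lost evidence on dose proportionality carry weight, because neither document makes it an objective or a planned analysis, and the box plots would show the pattern in any case.

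**Conclusion.** The point holds as a minor inconsistency confined to one numerical table. SAP 2.4.6.1 as worded conflicts with Protocol Table 10 and with its own neighbouring sentences, and SAP 1.6 does not record the difference. What would be lost is the tabulation of the PK-parameter statistics by OZ439 dose. The graphical display by arm, the exposure-response test and the ECG predictions all remain.

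The size of the distortion is hypothetical. It requires the literal reading, dose proportionality, equal arms and the assumed within-arm CVs. Only the doses and the equal allocation come from the documents. The general conclusion, that a pooled column describes no single arm, needs only that exposure differs appreciably between doses.

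**What to change.** In SAP 2.4.6.1, replace the two-item bracket with the four arms: FQ alone; FQ + OZ439 300 mg; FQ + OZ439 600 mg; FQ + OZ439 1000 mg. Add that OZ439 parameters are tabulated for the three OZ439 arms only. This restores Protocol Table 10 and matches the rest of the section.

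If a pooled column is wanted for some purpose, show it beside the per-arm columns and declare it, with the reason, in SAP 1.6.

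The cost is a few words in the SAP and a table shell with one column per arm. It needs no new data, no new analysis and no protocol amendment.
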